1	Neutropenia	Medical claim with an ICD-10 code in the IP or non-IP setting for neutropenia (dichotomous) or event in the lab table where absolute neutrophil count is < 1,500 cells per μ L	MM diagnosis to 1 day prior to index date
1	Hypercalcemia	Medical claim with an ICD-10 code in the IP or non-IP setting for hypercalcemia (dichotomous) or an event in the lab table where corrected serum calcium is > 11.5 mg/dL	MM diagnosis to 1 day prior to index date
1	Hepatotoxicity	Medical claim with an ICD-10 code in the IP or non-IP setting for hepatotoxicity (dichotomous)	MM diagnosis to 1 day prior to index date

Objective	Variable	Definition	Assessment Period(s)
1	Renal failure	Medical claim with an ICD-10 code in the IP or non-IP setting for renal failure (dichotomous)	MM diagnosis to 1 day prior to index date
1	Amyloidosis	Medical claim with an ICD-10 code in the IP or non-IP setting for amyloidosis (dichotomous)	MM diagnosis to 1 day prior to index date
1	Hypertension	Medical claim with an ICD-10 code in the IP or non-IP setting for hypertension (dichotomous)	MM diagnosis to 1 day prior to index date
1	Extramedullary disease	Medical claim with an ICD-10 code in the IP or non-IP setting for extramedullary disease (dichotomous)	MM diagnosis to 1 day prior to index date
1	CCI score	CCI ¹⁷ (continuous and categorical): 0 (no comorbidities) 1 to 2 (mild) 3 to 4 (moderate) ≥ 5 (severe)	180 days prior to index date to index date
1	Myocardial infarction	Medical claim with an ICD-10 code in the IP or non-IP setting for myocardial infarction (dichotomous)	180 days prior to index date to index date
1	Congestive heart failure	Medical claim with an ICD-10 code in the IP or non-IP setting for congestive heart failure (dichotomous)	180 days prior to index date to index date
1	Peripheral vascular disease	Medical claim with an ICD-10 code in the IP or non-IP setting for peripheral vascular disease (dichotomous)	180 days prior to index date to index date
1	Cerebrovascular disease	Medical claim with an ICD-10 code in the IP or non-IP setting for cerebrovascular disease (dichotomous)	180 days prior to index date to index date

Objective	Variable	Definition	Assessment Period(s)
1	Dementia	Medical claim with an ICD-10 code in the IP or non-IP setting for dementia (dichotomous)	180 days prior to index date to index date

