			G62.89, G61.9, G62.9, H46.3, M54.10, M54.18, M79.2, R20.0, R20.1, R20.2, R20.3, R20.8, R20.9	
Any infection	Baseline characteristic - Clinical	Claims data	An ICD-10 Diagnosis Code for any of the following types of infections. See the rows below for codes for each infection type. COVID-19, Adenoviral pneumonia, Cytomegaloviral pneumonitis, Other Pneumonia, Upper respiratory tract infection, Sepsis, Cytomegaloviral infection, PJP, Hepatitis C, Hepatitis B, Other infectious hepatitis, Helicobacter pylori, Candida esophagitis, Urinary tract infection	N/A
Use of intravenous anti-infective	Baseline characteristic - Clinical	Claims data	See “Antivirals,” “Antibiotics,” and “Antifungals” and where service category = injection/infusion drugs or where route = injectable or route array has injectable in it OR HCPCS/CPT codes that indicate IV administration of an anti-infective	N/A
Absolute neutrophil count (for Neutropenia)	Baseline characteristic - Clinical, AE	Claims data	White blood cell count x the percentage of neutrophils White blood cell count: Results_value in the lab results table where the result_abbrev is wbc and result_units are thousand per μ L Percent Neutrophil: Results_value in the lab results table where the result_abbrev is neutrophils percent and result_units are percent White blood cell count and percent neutrophil results must occur on the same day	Severe Chronic Neutropenia International Registry
Neutropenia	Baseline characteristic - Clinical, AE	Claims data	ICD-10 Diagnosis: D70.x or Absolute neutrophil count < 1500 cells per μ L	Kim et al. (2022) Lustberg et al. (2012)

PFIZER CONFIDENTIAL

Redacted

Hypercalcemia	Baseline characteristic - Clinical	Claims data	ICD-10 Diagnosis: E83.52 or value in the GDD table where test is hypercalcemia and result_units are mg/dL and result_value is > 11.5	Kumi et al. (2024) CTCAE v6 (2020)
Hepatotoxicity	Baseline characteristic - Clinical, AE	Claims data	ICD-10 Diagnosis: K71.x	Banerjee et al. (2023)
Amyloidosis	Baseline characteristic - Clinical	Claims data	ICD-10 Diagnosis: E85.4x, E85.8x, E85.9x	Quock et al. (2018)
Hypertension	Baseline characteristic - Clinical	Claims data	ICD-10 Diagnosis: I10x-I15x	Angier et al. (2019)
Extramedullary plasmacytoma	Baseline characteristic - Clinical	Claims data	ICD-10 Diagnosis: C90.2x	Ellington et al. (2021)
CCI score	Baseline characteristic - Clinical	Claims data	See components below	Glasheen et al. (2019)

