Diabetes with chronic complications	Baseline characteristic - Clinical	Claims data	ICD-10 Diagnosis: E08.2x, E08.3x, E08.4x, E08.5x, E09.2x, E09.3x, E09.4x, E09.5x, E10.2x, E10.3x, E10.4x, E10.5x, E11.2x, E11.3x, E11.4x, E11.5x, E13.2x, E13.3x, E13.4x, E13.5x	Glasheen et al. (2019)

PFIZER CONFIDENTIAL

Redacted

Mild or moderate renal disease	Baseline characteristic - Clinical	Claims data	ICD-10 Diagnosis: I12.9, I13.0, I13.10, N03.x, N05.x, N18.1, N18.2, N18.3, N18.4, N18.9, Z94.0	Glasheen et al. (2019)
Severe renal disease	Baseline characteristic - Clinical	Claims data	ICD-10 Diagnosis: I12.0, I13.11, I13.2, N18.5, N18.6, N19.x, N25.0, Z49.x, Z99.2	Glasheen et al. (2019)
Hemiplegia or paraplegia	Baseline characteristic - Clinical	Claims data	ICD-10 Diagnosis: G04.1, G11.4, G80.0, G80.1, G80.2, G81.x, G82.x, G83.x	Glasheen et al. (2019)
Human immunodeficiency virus	Baseline characteristic - Clinical	Claims data	ICD-10 Diagnosis: B20.x	Glasheen et al. (2019)
Metastatic solid tumor	Baseline characteristic - Clinical	Claims data	ICD-10 Diagnosis: C77.x, C78.x, C79.x, C80.0, C80.2	Glasheen et al. (2019)
Any malignancy	Baseline characteristic - Clinical	Claims data	ICD-10 Diagnosis: C0x.x, C1x.x, C2x.x, C30.x, C31.x, C32.x, C33.x, C34.x, C37.x, C38.x, C39.x, C40.x, C41.x, C43.x, C45.x, C46.x, C47.x, C48.x, C47.x, C48.x, C49.x, C50.x, C51-C58.x, C60-C63.x, C76.x, C80.1, C81.x, C82.x, C83.x, C84.x, C85.x, C88.x, C9x.x	Glasheen et al. (2019)
Albumin serum	Baseline characteristic - Lab	Claims data	An event in the lab results table where the result_abbrev is albumin serum and result_units are g per dL	
ALT	Baseline characteristic - Lab	Claims data	An event in the lab results table where the result_abbrev is ALT and result_units are IU per L	
AST	Baseline characteristic - Lab	Claims data	An event in the lab results table where the result_abbrev is AST and result_units are IU per L	
Neutrophil count	Baseline characteristic - Lab	Claims data	An event in the lab results table where the result_abbrev is neutrophils count and result_units are thousand per μ L	

PFIZER CONFIDENTIAL

Redacted

Creatinine	Baseline characteristic - Lab	Claims data	An event in the lab results table where the result_abbrev is creatinine serum and result_units are mg per dL	
Hemoglobin	Baseline characteristic - Lab	Claims data	An event in the lab results table where the result_abbrev is hemoglobin and result_units are g per dL	

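### Annex 2 derives the neutrophil count for neutropenia only from a same-day white-cell and percent pair, bypasses the directly reported count, and writes no conversion to the cells-per-µL cut-off

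*Protocol*

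**What the plan says.** Neutropenia is a baseline characteristic under Objective 1. Protocol Section 9.3, Table 2 defines it by a diagnosis code or an "event in the lab table where absolute neutrophil count is < 1,500 cells per" µL, assessed from MM diagnosis to the day before index.

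Annex 2 makes this operational in two rows, each assigned to both the baseline characteristic and the adverse event:

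- The ANC row gives "White blood cell count x the percentage of neutrophils". The white-cell input is "Results_value in the lab results table where the result_abbrev is wbc and result_units are thousand per" µL. The neutrophil input is "Results_value in the lab results table where the result_abbrev is neutrophils percent and result_units are percent". It adds that "White blood cell count and percent neutrophil results must occur on the same day".
- The neutropenia row accepts ICD-10 D70.x or "Absolute neutrophil count < 1500 cells per" µL.

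A separate Annex 2 row, used for the baseline laboratory table, extracts the neutrophil count as reported by the laboratory: "An event in the lab results table where the result_abbrev is neutrophils count", in thousand per µL. Table 2 lists the same variable in the same unit, over the 180 days to index. The ANC row does not refer to it.

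**The concern.** **Missed patients.** Table 2 read alone would let any low neutrophil count in the laboratory data qualify. Annex 2 narrows this to a count computed from two other results on one day. A direct count is the most immediate evidence of neutropenia in the data, and the study already holds it, yet it cannot trigger the flag.

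**Unwritten conversion.** The inputs are stored values in thousand per µL and percent, while the cut-off is in cells per µL. No factor links them. The other Annex 2 laboratory cut-offs are written on the stored scale: lymphocytes below 1.5 in thousand per µL, hemoglobin below 10.0 g per dL, IgG at or below 400 mg per dL, potassium below 3.0 mmol per L, calcium above 11.5 mg/dL. Neutropenia is the one that needs a conversion, so a programmer who follows the pattern of the Annex would get it wrong.

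**What is at stake.** The variable is a yes/no flag over a long look-back, so a single pair anywhere in that window can set it. Section 9.7.1 also plans to describe baseline characteristics in patients with and without a laboratory observation. A laboratory route that misses or over-flags patients would distort that description directly.

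**Working it through.** The plan states no figure to reproduce, so the check is unit arithmetic plus a reading of which patients the rule can reach.

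**1. Inputs (Annex 2).** W = white-cell count in thousand per µL; P = neutrophils in percent; cut-off 1500 cells per µL.

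**2. Three ways to evaluate the product.**

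- Units carried: ANC = W x 1000 x P/100 = W x P x 10 cells per µL.
- Bare product of stored values: W x P.
- Percent as a fraction, thousands not converted: W x P/100.

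| W | P | Units carried | Bare product | Fraction only |
|---|---|---|---|---|
| 5.0 | 60 | 3000, not flagged | 300, flagged | 3.0, flagged |
| 2.0 | 60 | 1200, flagged | 120, flagged | 1.2, flagged |
| 20 | 75 | 15,000, not flagged | 1500, not flagged | 15, flagged |

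**3. Effective cut-off if units are dropped.** W x P < 1500 is the same as W x P x 10 < 15,000, so the bare product flags every true ANC below 15,000 cells per µL. The fraction version, W x P/100 < 1500, flags every true ANC below 1,500,000.

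**4. Share flagged under assumed distributions.** The documents give none. Assume W log-normal with median 3 to 8 thousand per µL and log-SD 0.5, and P normal with mean 60 and SD 15. With units carried, 39% of paired results are flagged at median 3, falling to 2.7% at median 8. The bare product flags 100% at median 3 and 98.3% at median 8. The fraction version flags 100% throughout.

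**5. Who the rule cannot reach, whatever the unit handling.** Take a direct count of 0.8 thousand per µL, that is 0.8 x 1000 = 800 cells per µL, below 1500.

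- D70.x code present: flagged.
- No code, but a same-day pair giving an ANC below 1500: flagged.
- No code and no same-day pair: not flagged, although the study's own laboratory extract shows a value below the cut-off.

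The size of the third group depends on how often a direct count appears without a same-day pair. The documents do not say.

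**The case against.** The strongest reply is that Annex 2 labels every quantity. White cells are in thousand per µL, neutrophils in percent, the cut-off in cells per µL. With those labels carried, the formula is correct, and 3.0 thousand per µL for the 5.0 and 60% example is a correct ANC on the scale the protocol uses for neutrophil counts elsewhere. No figure in the document is miscalculated, and nowhere does the protocol say that the product is compared unconverted. Section 9.8 requires review by a second analyst or scientist and by the Study Lead, and neutropenia in nearly every tested patient would be conspicuous.

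This reply stands against a stronger reading. A reader might infer that the plan scores almost every patient with the two tests as neutropenic. The documents do not support that: it happens only if the labels are ignored. The near-100% shares above measure a possible coding error and are no evidence that it was made.

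The reply does not remove the reason to write the factor down. Section 9.8 says that measures are coded from the algorithms in this protocol and that the protocol is strictly followed, and Annex 2 is that field-level specification.

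On the direct count, one can say that a same-day white-cell count with differential is a deliberate choice and that the loss is unquantified. Both are fair. Neither explains why a reported value below the cut-off should leave a patient classed as not neutropenic, and correct unit handling does not cure it.

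**Conclusion.** The point holds as a gap in the derivation. The definition and its cut-off are not shown to be wrong.

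- **Certain from the text:** the laboratory route uses only the derived ANC, and a patient with a low direct count, no same-day pair and no D70.x code is missed. The direction is under-ascertainment; the size is unknown.
- **Conditional:** if the stored values were multiplied and compared with 1500 unconverted, the effective cut-off would be a true ANC of 15,000 cells per µL. Under the assumed distributions, 98.3% to 100% of paired results would then be flagged, against 2.7% to 39% with units carried.
- **Reach:** the laboratory route only; D70.x is untouched. One of many descriptive baseline variables is affected, together with an adverse event under Exploratory Objective 1, to which Annex 2 also assigns the rule. Eligibility, resource use, costs, time to discontinuation, TTNT/D and OS do not use it. The neutropenia row of Table 3 carries the lymphopenia definition; that is a separate fault and lends no weight here.

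This is a free improvement; the results do not depend on it enough to call it a required correction.

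**What to change.** In the Annex 2 ANC row, write:

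1. Where a directly reported neutrophil count exists, ANC (cells per µL) = that value in thousand per µL x 1000.
2. Otherwise, ANC (cells per µL) = white-cell count (thousand per µL) x percent neutrophils x 10, from same-day results.
3. Apply the existing cut-off of 1500 cells per µL to that value.

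State that the direct count is searched over the neutropenia assessment window. For baseline, Table 2 runs that window from MM diagnosis to the day before index, whereas the neutrophil count row covers only 180 days.

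Then check the code already run. One test record is enough for the units (5.0 and 60% must return 3000 and no flag) and one for the direct count (0.8 thousand per µL with no pair and no code must be flagged). Reporting how many patients qualify only through the direct count would show the size of the loss.

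The cost is one line of text and a short programming check. Section 6 places refresh 4 on 20 December 2025 and the final report on 28 February 2026, both after the 31 July 2025 version date, so the change could still be carried into them.

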1	Antifungal Medication ¹	Medical claim with an NDC, HCPCS, generic name or CPT code in the IP, non-IP, or pharmacy setting for antifungal medications (dichotomous)	14 days prior to index date to 1 day prior to index date Index date to the end of follow-up
1	Intravenous immunoglobulin ¹	Medical claim with an NDC, HCPCS, generic name, CPT, or ICD-10 procedure code in the IP, non-IP, or pharmacy setting for intravenous	14 days prior index date to 1 day prior to index date

Objective	Variable	Definition	Assessment Period(s)
		immunoglobulin administration (dichotomous)	Index date to the end of follow-up
1	Other hematological malignancies	Medical claim with an ICD-10 code in the IP or non-IP setting for hematological malignancies other than MM (dichotomous)	MM diagnosis to 1 day prior to index date
1	Any non-hematological malignancy	Medical claim with an ICD-10 code in the IP or non-IP setting for non-hematological malignancies (dichotomous)	MM diagnosis to 1 day prior to index date
1	Plasma cell leukemia	Medical claim with an ICD-10 code in the IP or non-IP setting for plasma cell leukemia (dichotomous)	MM diagnosis to 1 day prior to index date
1	Bone lesions	Medical claim with an ICD-10 code in the IP or non-IP setting for bone lesions (dichotomous)	MM diagnosis to 1 day prior to index date
1	Peripheral neuropathy	Medical claim with an ICD-10 code in the IP or non-IP setting for peripheral neuropathy (dichotomous)	MM diagnosis to 1 day prior to index date
1	Any infection	Medical claim with an ICD-10 code in the IP or non-IP setting for any infection of the following types (dichotomous): COVID-19 Sinusitis Bronchitis Adenoviral pneumonia Cytomegaloviral pneumonitis Other Pneumonia Upper respiratory tract infection	MM diagnosis to 1 day prior to index date

Objective	Variable	Definition	Assessment Period(s)
		
Sepsis
 
Cytomegaloviral infection
 
Pneumocystis jiroveci pneumonia (PJP)
 
Hepatitis C
 
Hepatitis B
 
Other infectious hepatitis
 
Helicobacter pylori
 
Candida esophagitis
 
Urinary tract infection
	
1	Use of intravenous anti-infective	Medical claim with an NDC code generic name, CPT, or HCPCS code in the IP, non-IP, or pharmacy setting for anti-infective where the route of administration is intravenous for an intravenous anti-infective (dichotomous)	MM diagnosis to 1 day prior to index date

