Exploratory Obj 1	Muscle spasms ³	Medical claim with an ICD-10 code in the IP, non-IP, or pharmacy setting for muscle spasms (dichotomous)	Index date to end of follow-up, where follow-up will be based on last dose of elranatamab (eg, 14 days after last recorded dose or 90 days after last recorded dose). See Section 9.7.6 for censoring criteria
Exploratory Obj 1	Musculoskeletal pain ³	Medical claim with an ICD-10 code in the IP, non-IP, or pharmacy setting for musculoskeletal pain (dichotomous)	Index date to end of follow-up, where follow-up will be based on last dose of elranatamab (eg, 14 days after last recorded dose or 90 days after last recorded dose). See Section 9.7.6 for censoring criteria
Exploratory Obj 1	COVID-19 ²	Medical claim with an ICD-10 code in the IP, non-IP, or pharmacy setting for COVID-19 (dichotomous)	Index date to end of follow-up, where follow-up will be based on last dose of elranatamab (eg, 14 days after last recorded dose or 90 days after last recorded dose). See Section 9.7.6 for censoring criteria
Infections			
Exploratory Obj 1	Sinusitis	Medical claim with an ICD-10 code in the IP, non-IP, or pharmacy setting for sinusitis (dichotomous)	Index date to end of follow-up, where follow-up will be based on last dose of elranatamab (eg, 14 days after last recorded dose or 90 days after last recorded dose).

			See Section 9.7.6 for censoring criteria
Exploratory Obj 1	Bronchitis	Medical claim with an ICD-10 code in the IP, non-IP, or pharmacy setting for bronchitis (dichotomous)	Index date to end of follow-up, where follow-up will be based on last dose of elranatamab (eg, 14 days after last recorded dose or 90 days after last recorded dose). See Section 9.7.6 for censoring criteria
Exploratory Obj 1 Exploratory Obj 1	Pneumonia ²	Medical claim with an ICD-10 code in the IP, non-IP, or pharmacy setting for pneumonia (dichotomous)	Index date to end of follow-up, where follow-up will be based on last dose of elranatamab (eg, 14 days after last recorded dose or 90 days after last recorded dose). See Section 9.7.6 for censoring criteria
Exploratory Obj 1	Adenoviral pneumonia ²	Medical claim with an ICD-10 code in the IP, non-IP, or pharmacy setting for adenoviral pneumonia (dichotomous)	Index date to end of follow-up, where follow-up will be based on last dose of elranatamab (eg, 14 days after last recorded dose or 90 days after last recorded dose). See Section 9.7.6 for censoring criteria

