Exploratory Obj 1	Cytomegaloviral pneumonitis ²	Medical claim with an ICD-10 code in the IP, non-IP, or pharmacy setting for cytomegaloviral pneumonitis (dichotomous)	Index date to end of follow-up, where follow-up will be based on last dose of elranatamab (eg, 14 days after last recorded dose or 90 days after last recorded dose).

			
See Section 9.7.6 for censoring criteria

Exploratory Obj 1	Other pneumonia ²	Medical claim with an ICD-10 code in the IP, non-IP, or pharmacy setting for pneumonia other than adenoviral or cytomegaloviral pneumonia (dichotomous)	
Index date to end of follow-up, where follow-up will be based on last dose of elranatamab (eg, 14 days after last recorded dose or 90 days after last recorded dose).
 
See Section 9.7.6 for censoring criteria

Exploratory Obj 1	Upper respiratory tract infection ²	Medical claim with an ICD-10 code in the IP, non-IP, or pharmacy setting for upper respiratory tract infection (dichotomous)	
Index date to end of follow-up, where follow-up will be based on last dose of elranatamab (eg, 14 days after last recorded dose or 90 days after last recorded dose).
 
See Section 9.7.6 for censoring criteria

Exploratory Obj 1	Sepsis ²	Medical claim with an ICD-10 code in the IP, non-IP, or pharmacy setting for sepsis (dichotomous)	
Index date to end of follow-up, where follow-up will be based on last dose of elranatamab (eg, 14 days after last recorded dose or 90 days after last recorded dose).
 
See Section 9.7.6 for censoring criteria

Exploratory Obj 1 Exploratory Obj 1	Cytomegaloviral infection ²	Medical claim with an ICD-10 code for PJP (dichotomous)	
Index date to end of follow-up, where follow-up will be based on last dose of elranatamab (eg, 14 days after last recorded dose or 90 days after last recorded dose).
 
See Section 9.7.6 for censoring criteria

Exploratory Obj 1	PJP ²	Medical claim with an ICD-10 code for PJP (dichotomous)	Index date to end of follow-up, where follow-up will be based on last dose of elranatamab (eg, 14 days after last recorded dose or 90 days after last recorded dose). See Section 9.7.6 for censoring criteria

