Musculoskeletal pain	AE	Claims data	ICD-10 Diagnosis: M25.50, M25.522, M25.551, M25.552, M25.561, M25.562, M25.572, M25.579, M25.59, M25.612, M25.621, M25.629, M25.631, M25.641, M25.642, M25.652, M25.661, M25.662, M25.669, M25.671, M25.673, M25.674, M25.675, M25.676, M54.6, M54.81, M79.1, M79.12, M79.18, M79.621, M79.622, M79.631, M79.639, M79.641, M79.644, M79.646, M79.652, M79.659, M79.661, M79.662, M79.669, M79.671, M79.673, M79.675, M25.511, M25.512, M25.519, M25.521, M25.529, M25.531, M25.532, M25.539, M25.541, M25.542, M25.549, M25.559, M25.569, M25.571, M25.60, M25.611, M25.619, M25.622, M25.632, M25.639, M25.649, M25.651, M25.659, M25.672, M25.69, M54.89, M54.9, M79.10, M79.11, M79.601, M79.602, M79.603, M79.604, M79.605, M79.606, M79.609, M79.629, M79.632, M79.642, M79.643, M79.645, M79.651, M79.672, M79.674, M79.676	Clinical Classifications Software Refined for ICD-10-CM
COVID-19	AE - infection	Claims data	ICD-10 Diagnosis: U07.1	Pfaff et al. (2023)
Adenoviral pneumonia	AE - infection	Claims data	ICD-10 Diagnosis: J12.0	Cocoros et al. (2024)

Cytomegaloviral pneumonitis	AE - infection	Claims data	ICD-10 Diagnosis: B25.0	ICD-10data.com
Other pneumonia	AE - infection	Claims data	ICD-10 Diagnosis: J12.1, J12.2, J12.81, J12.3, J12.89, J12.9, J13, J18.1, J15.0, J15.1, J14, J15.4, J15.3, J15.20, J15.211, J15.212, J15.29, J15.8, J15.5, J15.6, A48.1, J15.9, J15.7, J16.0, J16.8, A37.01, A37.11, A37.81, A37.91, A22.1, B44.0, J17, B77.81, J18.0, J18.8, J18.9, J10.00, J10.01, J10.08, J11.00, J11.08	Smithee et al. (2020)
Pneumonia	AE - infection	Claims data	An ICD-10 Diagnosis Code for any of the following types of pneumonia. See the following rows for infection type: Adenoviral pneumonia, cytomegaloviral pneumonia, other pneumonia	
Upper respiratory tract infection	AE - infection	Claims data	ICD-10 Diagnosis: A38.0-A38.9, J02.0-J03.91, J01.00-J01.91, J09.x1-J11.89, J00, J04.0-J06.9, H65.00-H65.199, H68.011-H68.019, J20.0-J20.9, J45.20-J45.998, J45.21, J45.31, J45.41, J45.51, J45.901	Butler et al. (2023)
Acute sinusitis	AE - infection	Claims data	ICD-10 Diagnosis: J01.x0	Savage et al. (2023)
Bronchitis	AE - infection	Claims data	ICD-10 Diagnosis: J20.0-J20.9	Butler et al. (2023)
Sepsis	AE - infection	Claims data	ICD-10 Diagnosis: A02.1, A22.7, A26.7, A32.7, A40.0, A40.1, A40.3, A40.8, A40.9, A41.01, A41.02, A41.1, A41.2, A41.3, A41.4, A41.50, A41.51, A41.52, A41.53, A41.59, A41.81, A41.89, A41.9, A42.7, A54.86, B37.7, R65.20, R65.2	Prasad et al. (2021)

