Cytomegaloviral disease (including cytomegaloviral infection)	AE - infection	Claims data	ICD-10 Diagnosis: B25.x	Grosse et al. (2022)
PJP	AE - infection	Claims data	ICD-10 Diagnosis: B59	Boone et al. (2022)

PFIZER CONFIDENTIAL

Redacted

Hepatitis C	AE - infection	Claims data	ICD-10 Diagnosis: B17.1x, B18.2, B19.2x	Kim et al. (2018)
Hepatitis B	AE - infection	Claims data	ICD-10 Diagnosis: B16.x, B17.0, B18.0, B18.1, B19.1x	Kim et al. (2018)
Other infectious hepatitis	AE - infection	Claims data	ICD-10 Diagnosis: B17.2, B17.8, B17.9, B18.8, B18.9, B19.0, B19.9, B26.81, B58.1	Lo et al. (2021)
Helicobacter pylori	AE - infection	Claims data	ICD-10 Diagnosis: B96.81	Shah et al. (2023)
Candida esophagitis	AE - infection	Claims data	ICD-10 Diagnosis: B37.81	Gold et al. (2024)
Urinary tract infection	AE - infection	Claims data	ICD-10 Diagnosis: N39.0	Papp et al. (2023)

PFIZER CONFIDENTIAL

Redacted

Redacted

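### Annex 2 leaves B59 out of the Pneumonia adverse event, so a patient whose only pneumonia code is B59 counts as PJP but not as pneumonia, contrary to Table 3

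*Protocol*

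**What the plan says.** Table 3 (Protocol section 9.3) has a Pneumonia row with no restriction on type: "Medical claim with an ICD-10 code in the IP, non-IP, or pharmacy setting for pneumonia (dichotomous"). It also has an Other pneumonia row, defined as "pneumonia other than adenoviral or cytomegaloviral pneumonia (dichotomous"). Only two types are carved out there. Adenoviral pneumonia, cytomegaloviral pneumonitis and PJP each have a separate row as well. The baseline infection list in Table 2 of the same section spells the last of these out as "Pneumocystis jiroveci pneumonia (PJP").

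Annex 2 gives the codes:

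- Adenoviral pneumonia: "ICD-10 Diagnosis: J12.0".
- Cytomegaloviral pneumonitis: "ICD-10 Diagnosis: B25.0".
- Other pneumonia: a list of 41 codes, ending in "A22.1, B44.0, J17, B77.81, J18.0, J18.8, J18.9, J10.00, J10.01, J10.08, J11.00, J11.08".
- Pneumonia: any code from "Adenoviral pneumonia, cytomegaloviral pneumonia, other pneumonia".
- PJP: "ICD-10 Diagnosis: B59".

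Section 9.7.6 reports prevalence and incidence with 95% confidence intervals for every adverse event in Table 3. Footnote 2 to that table gives Pneumonia, Other pneumonia and PJP a 60-day washout for incident cases. Section 9.8 says that variables will be coded from the codes in the protocol and that the protocol will be strictly followed.

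**The concern.** The words of Table 3 and the codes of Annex 2 describe different variables. By the words, PJP belongs in Pneumonia and also in Other pneumonia. By the codes, it is in neither. Because section 9.8 ties the programming to the listed codes, the reported figure will follow Annex 2, while a reader of the results will take the label at its Table 3 meaning.

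Three results are affected, in the elranatamab cohort and the teclistamab cohort alike:

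- Prevalence of Pneumonia and of Other pneumonia can only be too low, because patients with B59 alone are left out of the numerator.
- Incidence misses the same events in follow-up. In addition, a patient whose only pneumonia code in the 60-day washout is B59 is treated as free of pneumonia at baseline, so a later listed code would count as incident. This second effect runs the other way.
- Time to pneumonia onset misses the same events if onset is analysed by infection type.

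**Working it through.** The plan states no figure to reproduce, so the check is one of set membership, followed by a scale for the effect.

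**Step 1: the codes in the composite (Annex 2).**

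| Component row | Codes | Contains B59? |
|---|---|---|
| Adenoviral pneumonia | J12.0 (1 code) | No |
| Cytomegaloviral pneumonitis | B25.0 (1 code) | No |
| Other pneumonia | 41 codes | No |
| Union = Pneumonia | 1 + 1 + 41 = 43 distinct codes | No |

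The only codes in the union that begin with B are B25.0, B44.0 and B77.81. With B59 added, the union would have 44 codes.

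**Step 2: how three kinds of patient are classified.**

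| Codes in the window | PJP row | Pneumonia by Annex 2 | Pneumonia by the words of Table 3 |
|---|---|---|---|
| B59 only | Yes | No | Yes |
| B59 and a listed code, e.g. J18.9 | Yes | Yes | Yes |
| A listed code only | No | Yes | Yes |

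The two definitions differ only in the first line.

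**Step 3: size.** Section 9.7.6 defines prevalence as 100 × (patients with an event) / (patients in the cohort). If k patients in a cohort of N have B59 and none of the 43 listed codes, the shortfall is 100 × k / N percentage points. The documents do not give k. The only elranatamab count is 56 patients with a claim (section 9.5), used here as an illustrative N:

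- k = 1: 100 × 1 / 56 = 1.79 points
- k = 2: 100 × 2 / 56 = 3.57 points
- k = 3: 100 × 3 / 56 = 5.36 points

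The 56 are claimants before the eligibility criteria are applied, at an early data cut. The analysed cohort may be smaller or, after the quarterly refreshes, larger. The shift per patient is 100 / N and shrinks as N grows.

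**The case against.** The best defence is that this is a grouping choice. The infection lists show PJP beside the pneumonia entries, not beneath them. Table 3 refers the reader to Annex 2 for the full code list, and Annex 2 names the three components explicitly, so the variable is reproducible even if the Table 3 label is loose. That does not reconcile the two places. Adenoviral pneumonia and cytomegaloviral pneumonitis also have their own rows, yet both are counted in the composite, so a separate row is not the protocol's reason for leaving a type out. Nowhere does the protocol say that PJP is excluded, and the Table 3 wording of Other pneumonia includes it.

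Other parts of the defence stand. A reader might infer that PJP is never counted as pneumonia, or that it drops out of the safety results. The documents do not support either. A PJP patient with any of the 43 listed codes is in the composite, and PJP keeps its own prevalence and incidence and its place in the baseline any-infection variable and in time to infection onset. A reader might also infer that a large share of all pneumonia is missed. That share depends on how often B59 occurs alone and on how often listed codes occur, and the protocol gives neither.

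The stakes are also limited. Adverse events fall under Exploratory Objective 1, the study makes no formal comparison between groups (section 9.7), and section 9.9 already warns of coding misclassification and wide intervals.

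**Conclusion.** The inconsistency is real and follows from the code lists alone. Annex 2 codes a patient with B59 only as having no pneumonia, and Table 3 codes the same patient as having it. Prevalence of Pneumonia and Other pneumonia is understated wherever such patients exist. Incidence loses the same events, with a possible small offset through the washout. The number of such patients cannot be derived from the documents and could be zero. On the illustrative denominator of 56, each one is worth about 1.8 percentage points of prevalence. This is a minor point on an exploratory, descriptive safety outcome, and no primary objective depends on it.

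**What to change.** Add the PJP row (B59) to the Annex 2 Pneumonia composite, keep PJP as a row of its own, and reword Other pneumonia in Table 3 as pneumonia other than adenoviral, cytomegaloviral or PJP. The four component rows then cover the composite, and Table 3 agrees with Annex 2.

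If the sponsor meant to leave PJP out, the alternative is to label both Pneumonia and Other pneumonia as excluding PJP in Table 3, Annex 2 and the results tables.

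The first option costs one code and a re-run of the affected rows on data already held. Reported pneumonia prevalence can only stay the same or rise. The second option costs wording alone. If the definition changes between refreshes, earlier pneumonia figures built on the 43-code list should be re-run or footnoted so that the series stays comparable up to the final report.
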